**PAGE 32/139** 

(UTI) due to impaired voiding following BTX-A treatment, which is observed in subjects not performing CIC.

In addition to BTX-A bladder-naive subjects who have never previously received intradetrusor BTX-A for UI, the study will also enrol BTX-A bladder-non-naive subjects, who have previously received intradetrusor BTX-A for NDO. This will reflect real world usage and it has been demonstrated previously that treatment response does not vary significantly following retreatment in subjects treated with intradetrusor BTX-A for UI due to NDO [18]. In order to be eligible for entry into the study, more than 9 months must have elapsed since any previous intradetrusor BTX-A treatment administration.

### 1.7 Placebo Usage During Treatment 1

The use of placebo during the first IMP treatment administration ensures a rigorous, scientifically appropriate study design to assess the efficacy and safety of Dysport® in the treatment of UI due to NDO. The use of placebo is justified because:

- Although UI due to NDO is a symptomatic condition, which can lead to significantly impaired quality of life, it is not life-threatening. Therefore, a single administration of placebo with the opportunity to receive active IMP treatment from as early as 12 weeks later ensures that all subjects have the opportunity to receive the active IMP without prolonged delay. All further study treatment administrations will be active IMP, for up to 2 years post randomisation, ensuring all subjects also have the opportunity to be treated with active IMP multiple times during the study, if required.
- Treatment with BTX-A may be associated with an increased risk of UTIs in an NDO population that is already susceptible to UTIs. In order to accurately estimate the true incidence of UTIs associated with the active IMP, compared to the background incidence and the incidence due to the treatment administration procedure, a placebo group comparison is required.
- OnabotulinumtoxinA, is not authorised or marketed for the treatment of UI due to NDO in all the planned countries where this Dysport® phase 3 program is to be conducted; therefore, its use as an active comparator in these countries would not be appropriate. An objective of this program is to confirm the efficacy of Dysport® in this indication

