Statistical Analysis Plan

Version: Final v1.0

September-2018

Ipsen Protocol No. D-FR-52120-223

000000146513

Date of Issue: 21-

Covance Study ID:

-
- any UTI TEAEs
 - UTI TEAEs leading to withdrawal
 - serious UTI TEAEs
 - TEAE leading to death

In view of the anticipated difference in duration of the Dysport and placebo treatment cycles, this overview table will also be provided including only TEAEs occurring up to 12 weeks after first IMP treatment administration.

A similar overview table will be produced for the number and percentage of subjects with at least one of the following events occurred pre-treatment for randomised subjects. The number of occurrences of the following events will be presented as well.

- any AE
 - Intensity of AE (mild, moderate, severe)
- any SAE
 - any SAEs leading to withdrawal
- AE leading to death

TEAEs will be summarised overall, for DPBC cycle, and Dysport Cycles with the number and percentage of subjects with TEAEs presented by primary SOC and PT. In addition, this table will be provided including only TEAEs occurring any time after first dose of IMP until up to 12 weeks after first IMP treatment administration. This will also be summarised by aetiology of NDO.

For AESIs, summary tables may also be produced following medical review of available information.

The same summaries for overall, for DBPC Cycle, and Dysport Cycles with the number and percentage of subjects with TEAEs presented by primary SOC and PT will be presented for serious TEAEs, IMP-related TEAEs, TEAEs leading to withdrawal, TEAEs of special interest, and other protocol defined TEAEs. TEAEs with PTs observed in $\geq 1\%$, $\geq 2\%$, and $\geq 5\%$ of subjects and IMP-related TEAEs with PTs observed in $\geq 1\%$, $\geq 2\%$, and $\geq 5\%$ of subjects will be summarised as well.

Additionally, TEAEs will be tabulated by decreasing overall PT frequency and intensity in each SOC and PT category.

The above will also be presented for SAEs.

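### In the placebo-controlled cycle, the SOC/PT tables of serious, IMP-related, withdrawal, AESI and UTI events and the threshold tables have no stated 12-week version, so unequal cycle length can appear as a Dysport excess

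*SAP*

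**What the plan says.** SAP 7.7.1 builds the adverse event tables in layers.

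- **Overview table.** It carries lines for any, IMP-related, serious, special-interest (AESI), UTI and fatal TEAEs, with withdrawal sub-lines. It is produced for the placebo-controlled (DBPC) cycle, the Dysport cycles and overall. The SAP then adds a fixed window. Its reason is worded "In view of the anticipated difference in duration of the Dysport and placebo treatment cycles". Its remedy is that "this overview table will also be provided including only TEAEs occurring up to 12 weeks after first IMP treatment administration".
- **All TEAEs by SOC and PT.** Here too "this table will be provided including only TEAEs occurring any time after first dose of IMP until up to 12 weeks" after the first administration.
- **Subset tables by SOC and PT.** "The same summaries for overall, for DBPC Cycle, and Dysport Cycles with the number and percentage of subjects with TEAEs presented by primary SOC and" preferred term are planned for serious, IMP-related, withdrawal, AESI and other protocol-defined TEAEs. SAP 3.3 shows that the last group is UTI. The periods are listed, and 12 weeks is not among them.
- **Threshold and intensity tables.** Terms (all TEAEs and IMP-related) reaching 1%, 2% and 5% "of subjects will be summarised as well". No window is named, nor is one named for the tables by PT frequency and intensity.

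Percentages use the number of subjects in the population for the cycle (SAP 7.1). Safety comparisons are descriptive only (Protocol synopsis, Safety endpoints). Protocol 1.7 gives one reason for the placebo arm: "In order to accurately estimate the true incidence of UTIs associated with the active IMP, compared to the background incidence".

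**The concern.** An event belongs to a cycle by its date of onset or worsening, and the DBPC cycle ends only at retreatment or end of study. It can therefore last from just over 12 weeks to about 104 weeks. A percentage of subjects with at least one event rises with the time at risk. If one arm is watched for longer, a background event with the same rate in every arm appears more often there.

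The SAP sees this and corrects for it in two tables. On the readable text the correction stops before the tables that show which serious, IMP-related or withdrawal terms exceed placebo, and which terms reach a reporting threshold. With no formal safety testing, readers will rely on these side-by-side percentages. The SAP already takes the same care for efficacy: SAP 7.6.3 and 7.6.6 stop between-group testing at Week 12 because later visits depend on retreatment.

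**Working it through.** The documents give no event rate, no expected cycle length and no safety power, so there is no stated figure to reproduce. The check has two parts.

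**1. Does anything else in the readable text equalise follow-up?** SAP 7.1 uses subjects as the denominator. SAP 7.5 totals exposure across the whole study up to the last attended visit, so for a subject who starts on placebo the total IMP exposure includes later Dysport time. No DBPC person-time or exposure-adjusted incidence is specified.

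**2. How large could the effect be?**

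*Direction.* The SAP anticipates a difference but does not say which arm is longer. SAP 2.2 makes retreatment depend on weekly UI exceeding 0.7 of baseline, and SAP 2.3 assumes reductions of 21 (Dysport) and 12 (placebo) at Week 6. At those reductions a subject with baseline B qualifies when 0.3B > 12, so B > 40 on placebo, and when 0.3B > 21, so B > 70 on Dysport. More placebo subjects should qualify early, so longer Dysport cycles are a reasonable inference.

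*Formula.* With a constant hazard h, equal in all arms, and a fixed cycle length T in weeks: h = −ln(1 − p12)/12 and P(event in cycle) = 1 − exp(−hT). Both p12 (the risk by Week 12) and T are assumptions.

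For p12 = 2%, h = 0.0202/12 = 0.00168 per week. Then 1 − exp(−0.00168 × 16) = 2.7% and 1 − exp(−0.00168 × 36) = 5.9%, a ratio of 2.2 with no drug effect. In this case the term passes the 5% cut on Dysport only.

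| 12-week risk, all arms | Placebo / Dysport cycle (weeks) | Placebo | Dysport |
|---|---|---|---|
| 1% | 16 / 36 | 1.3% | 3.0% |
| 2% | 16 / 24 | 2.7% | 4.0% |
| 2% | 16 / 36 | 2.7% | 5.9% |
| 2% | 16 / 48 | 2.7% | 7.8% |
| 5% | 16 / 36 | 6.6% | 14.3% |
| 20% | 16 / 36 | 25.7% | 48.8% |
| any | equal lengths | no difference | no difference |

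*Sensitivity to timing.* Let a fraction f of the 12-week cumulative hazard H = −ln(1 − p12) be confined to the first 12 weeks, with the rest continuing at a constant rate. Then P = 1 − exp(−fH − (1 − f)H × T/12). For p12 = 20% and cycles of 16 and 36 weeks:

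| f | Placebo | Dysport |
|---|---|---|
| 0 | 25.7% | 48.8% |
| 0.5 | 22.9% | 36.0% |
| 0.9 | 20.6% | 23.5% |
| 1.0 | 20.0% | 20.0% |

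For p12 = 2% (H = 0.0202) and f = 0.5, the exponents are 0.0101 + 0.0101 × 16/12 = 0.0236 and 0.0101 + 0.0101 × 36/12 = 0.0404. That gives 2.3% against 4.0%, and the 5% cut is no longer crossed.

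*After the fix.* With both arms cut at 12 weeks and equal hazards, the two percentages are equal for every assumed rate.

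**The case against.** Much is already available at equal time. The 12-week overview gives totals for every category named here, including UTI and serious UTI. The 12-week all-TEAE table gives every preferred term, so the 2% example would appear there as 2% in each arm. The purpose stated for UTI in Protocol 1.7 is therefore largely met. All of this stands, and it narrows the gap to the term-level breakdown within the serious, IMP-related, withdrawal and AESI subsets, the UTI group by term, and the threshold and intensity tables. An all-TEAE table cannot supply the subset breakdown, because it does not separate serious or related events within a term.

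The wording also leaves room. The subset sentence opens by referring back to summaries just described, which include a 12-week version, and the closing sentence of 7.7.1 extends what precedes it to SAEs. SAP section 1 says that the SAP includes a list of all outputs; that list is not readable in the public copy, so 12-week versions there cannot be ruled out. The explicit list of periods favours the narrower reading without settling it.

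Some subsets are less exposed. SAP 7.7.1 removes AESIs whose onset time does not fit the mechanism, and Protocol 8.1.2.2 counts a plausible time sequence towards relatedness. Both limit late background events. The difference in cycle length will also be visible, because SAP 7.6.6.4 reports time between treatments with Kaplan-Meier curves by arm.

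**Conclusion.** The point holds as a gap in specification. On the readable text, these DBPC-cycle tables have neither a 12-week version nor a person-time adjustment, and they can show a Dysport excess for events that continue after Week 12 even when rates are equal. The size illustrated is 2.7% against 5.9%. It rests on assumed cycles of 16 and 36 weeks, an assumed 2% risk by Week 12 and a constant hazard. It shrinks as events cluster around the procedure and is nil if all of them do.

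A reader might go further and infer that Dysport will show excess harm, or that drug effects cannot be told apart from longer follow-up. The documents support neither. They give no cycle lengths and no direction, and the two 12-week tables already show category totals and every term at equal time. No hypothesis test is affected, since safety is descriptive. The change is worth making because it costs little and extends the SAP's own safeguard.

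**What to change.** In SAP 7.7.1:

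- State that the DBPC-cycle SOC/PT tables of serious, IMP-related, withdrawal, AESI and UTI TEAEs, the PT-by-intensity tables and the 1%, 2% and 5% tables will also be produced for TEAEs up to 12 weeks after the first IMP administration. If the redacted list already has them, this one sentence removes the ambiguity.
- For the placebo-versus-Dysport comparison, select the terms in the threshold tables on 12-week incidence.
- Add exposure-adjusted rates for the DBPC cycle, using each subject's own time in that cycle.
- Keep the whole-cycle tables.

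The cost is SAP wording and a re-run of planned tables with a filter that the SAP already needs, plus the derivation of DBPC time from dates already collected. No new data are required. The downside is more output, and the 12-week versions omit later events, which remain visible in the whole-cycle tables.

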7.7.2 Laboratory Evaluations

Clinical laboratory data from the central laboratory (haematology, biochemistry and urinalysis, and urine culture and sensitivity) will be listed in Standard International (SI) units. Any unscheduled laboratory assessments will be included in the listings. For post-baseline, only data from scheduled visits will be included in the summary tables.

Haematology parameters:

- Red blood cell count
- Haemoglobin

Statistical Analysis Plan

Version: Final v1.0

September-2018

Ipsen Protocol No. D-FR-52120-223

000000146513

Date of Issue: 21-

Covance Study ID:

- Haematocrit
- Mean corpuscular volume
- Mean corpuscular hemoglobin
- Mean corpuscular hemoglobin concentration
- White blood cell count with differential (neutrophils, lymphocytes, monocytes, eosinophils, basophils, and others)
- Platelet count.

Serum Chemistry parameters:

- Urea, creatinine, total bilirubin, conjugated bilirubin
- Chloride, bicarbonate, sodium, potassium, calcium, inorganic phosphate
- Alkaline phosphatase, aspartate aminotransferase, alanine aminotransferase, gamma glutamyl transferase
- Albumin, total protein, total cholesterol, triglycerides, fasting glucose.

Urinalysis parameters:

- pH, protein, ketones, bilirubin, blood, urobilinogen, nitrites, leukocytes, glucose and specific gravity

Laboratory results will be classified as low, normal, or high at each visit according to the laboratory supplied reference ranges. Abnormal values will be flagged (High [H], Low [L]) in the data listings. A list of clinically significant abnormal values will be presented by treatment group and subject ID.

Descriptive statistics will be presented for actual values and changes from study baseline at each scheduled assessment by treatment group.

The number and percentage of subjects will be summarised for clinical significance of each abnormal value.

For each scheduled post-baseline assessment visit, shift from study baseline tables of the number and percentage of subjects with low, normal or high values will be presented.

7.7.3 Antibody Test

Antibody testing results will be presented in a data listing. The listings for subjects with at least one positive neutralising (baseline or post baseline) will be provided separately.

The number and percentage of subjects with the presence of neutralising BTX-A antibodies at study baseline, and post-baseline visits will be presented in the shift tables. The number of neutralising BTX-A antibodies seroconverters (subjects having a negative result at study baseline and at least one positive result at one post-treatment time point) and the time by when the subjects seroconverted will be reported.

7.7.4 Vital Signs

The normal ranges for the vital signs are displayed in Table 2 below:

Table 2 Vital Signs Normal Ranges

Parameter	Low	Normal	High
-----------	-----	--------	------

Statistical Analysis Plan

Version: Final v1.0
September-2018

Ipsen Protocol No. D-FR-52120-223
000000146513

Date of Issue: 21-

Covance Study ID:

Diastolic Blood Pressure (mmHg)	<40	40-110	>110
Systolic Blood Pressure (mmHg)	<60	60-190	>190
Heart Rate (bpm)	<50	50-130	>130
Height (cm)	<120	120-200	>200
Weight (kg)	<35	35-120	>120

Vital signs data will be presented in a listing by treatment group and subject. Any unscheduled vital signs assessment will be presented in the listings. Vital signs include blood pressure (systolic/diastolic), heart rate, respiratory rate and temperature.

Summary statistics will be presented for actual values and changes from study baseline at each scheduled assessment by treatment group.

The number and percentage of subjects with abnormal values (Low and High) will be presented by treatment group.

For the DBPC period and each Dysport Cycle, shift from study baseline tables of the number and percentage of subjects with low, normal or high values will be presented.

7.7.5 Electrocardiograms

Not applicable.

7.7.6 Other Safety Variables

Pregnancy test, urinary tract ultrasound and physical examination data will be presented in data listings.

7.8 Primary Analysis of the Study

CCI
[REDACTED]

The analysis will consist of all tables, figures and listings for the study described in this statistical analysis plan using all available data up to the cut-off date and a clinical study report will be written. A final analysis will occur when all subjects have completed the study (or at other timepoints if required to support regulatory agency submissions).

8 CHANGES IN PLANNED ANALYSES

Not applicable.

9 DATA ISSUES

Not applicable.

Statistical Analysis Plan

Version: Final v1.0

September-2018

Ipsen Protocol No. D-FR-52120-223

000000146513

Date of Issue: 21-

Covance Study ID:

